## **8 STUDY PROCEDURES**

### **8.1 Participant Registration**

Eligibility of each participant will be established prior to enrollment.

Informed consent *MUST* be completed prior to receiving any study related procedures.

Unless otherwise defined in the written protocol text, all procedures/assessments will be conducted in accordance with RPCI Clinical Research Services Standard Operating Procedures.

### **8.2 Baseline Evaluations**

The following will be performed within 2 weeks prior to first dose of study drug (unless otherwise noted):

- Medical history (including all prior anti-tumoral therapy related to colorectal cancer)
- Physical examination
- Vital signs (i.e., temperature, heart rate, respiratory rate, blood pressure, body weight, and height)
- Hematology (i.e., complete blood count (CBC) with automated differentials)
- Chemistry (i.e., complete metabolic panel (CMP): chloride, CO2, potassium, sodium, BUN, glucose, calcium, creatinine, total protein, albumin, total bilirubin, alkaline phosphatase, AST, ALT, A/G ratio, BUN/creatinine ratio, osmol (Calc), anion gap).
- Pregnancy test serum in females of childbearing potential
- Urine spot protein and urine spot creatinine levels (UPCR)
- Coagulation studies - INR/PT, PTT
- ECOG Performance Status (**Appendix B**)
- Concomitant Medications: List any medications that were ongoing, or stopped, within 1 week prior to first dose of study drug.
- Baseline imaging – CT chest/abdomen/pelvis (within 4 weeks)

**8.3 Evaluations Performed On Therapy (Day 1 of each cycle, +/- 3 days)**

- Physical examination
- Vital signs (i.e., temperature, heart rate, respiratory rate, blood pressure, body weight)
- Hematology (i.e., complete blood count (CBC) with automated differentials)
- Chemistry (i.e., complete metabolic panel (CMP): chloride, CO2, potassium, sodium, BUN, glucose, calcium, creatinine, total protein, albumin, total bilirubin, alkaline phosphatase, AST, ALT, A/G ratio, BUN/creatinine ratio, osmol (Calc), anion gap).
- Blood draw for PK and biomarker (first 32 patients only, on cycle 1 and 3). See sections **8.10** and **8.11** for collection time points.
- ECOG Performance Status (**Appendix B**)
- Concomitant Medications: List any ongoing medications with dose changes, as applicable.
- Adverse events
- CT scan of the chest/abdomen/pelvis with IV contrast (or if unable to receive IV contrast, a non-contrast CT of the chest + MRI of the abdomen/pelvis) every 9 weeks after Cycle- 1 Day 1 ( $\pm 7$  days)
- CEA:
  - Cycle 1 – Day 1
  - Cycle 4 – Day 1
  - Every 3 cycles (on Day 1) from Cycle 4 onward.
- Study Drug Reconciliation – Beginning with Cycle 2 – Day 1 (reconciliation for Cycle 1) and on Day 1 of all subsequent cycles prior to the initiation of a new cycle.

**8.4 Evaluations Performed On Therapy (Day 2 cycle 1)**

- Blood draw for PK (first 32 patients only)

**8.5 Evaluations Performed On Therapy (Day 8 of cycles 1 and 2, phase I only, +/- 3 days)**

- Physical examination
- Vital signs (i.e., temperature, heart rate, respiratory rate, blood pressure, body weight)
- Chemistry (i.e., complete metabolic panel (CMP): chloride, CO2, potassium, sodium, BUN, glucose, calcium, creatinine, total protein, albumin, total bilirubin, alkaline phosphatase, AST, ALT, A/G ratio, BUN/creatinine ratio, osmol (Calc), anion gap).
- Hematology (i.e., complete blood count (CBC) with automated differentials).
- Adverse events
- Concomitant Medications: List any ongoing medications with dose changes, as applicable.

**8.6 Evaluations Performed On Therapy (Day 15 of cycle 1)**

- Blood draw(s) for PK and biomarker (CAFs on first 32 patients only)

- Concomitant Medications: List any ongoing medications with dose changes, as applicable.
- Adverse events

### **8.7 Evaluations Performed at End of Treatment (30 +/- 7 days post last dose of study drug)**

The following evaluations will be performed following treatment discontinuation. In the case of persistent drug-related toxicity, patients will be followed every 28 days until resolution or satisfactory stabilization is achieved. Telephone contact is acceptable.

- Physical examination, including vital signs (i.e., temperature, heart rate, respiratory rate, blood pressure, body weight)
- Hematology (i.e., complete blood count (CBC) with automated differentials)
- Chemistry (i.e., complete metabolic panel (CMP): chloride, CO2, potassium, sodium, BUN, glucose, calcium, creatinine, total protein, albumin, total bilirubin, alkaline phosphatase, AST, ALT, A/G ratio, BUN/creatinine ratio, osmol (Calc), anion gap).
- Concomitant medication: List any ongoing medications with dose changes, as applicable
- Adverse events
- Drug reconciliation

### **8.8 Medical Record Review**

Every 6 months for overall survival.

### **8.9 Schedule of Procedures and Observations**

The schedule of procedures and observations for this study is summarized in **Table 11** (Phase I) and **Table 12** (Phase II) below.

**Note:** Except for cycle 1- day 1 and day 2 procedures, *all other procedures may be performed ± 3 days from the proposed date.* Disease assessment (CT imaging) may be performed up to 7 days prior to day 1 of the corresponding cycle.

**Table 11 Phase I: Schedule of Procedures and Observations**

| Evaluation   | Baseline  | Cycle 1 |   |   |    | Cycle 2 |   | Cycle 3 | Cycle 4 | Further Cycles  | End of Treatment  | Follow-Up  |
|--|-----------------------|---------|---|---|----|---------|---|---------|---------|-----------------|-------------------------------|------------------------|
|  |                       | 1       | 2 | 8 | 15 | 1       | 8 | 1       | 1       | 1               |                               |                        |
| Medical History  | X                     |         |   |   |    |         |   |         |         |                 |                               |                        |
| Pre-Existing Conditions  | X                     |         |   |   |    |         |   |         |         |                 |                               |                        |
| Physical Examination , including vital signs (i.e., temperature, heart rate, respiratory rate, blood pressure, body weight, and height)  | X                     | X       |   | X |    | X       | X | X       | X       | X               | X                             |                        |
| Hematology   | X                     | X       |   | X |    | X       | X | X       | X       | X               | X                             |                        |
| Chemistry    | X                     | X       |   | X |    | X       | X | X       | X       | X               | X                             |                        |
| INR/PT, PTT  | X                     |         |   |   |    |         |   |         |         |                 |                               |                        |
| CEA  |                       | X       |   |   |    |         |   |         | X       | X  |                               |                        |
| Urine Sample for Urine Protein Creatinine Ratio (UPCR)   | X                     |         |   |   |    |         |   |         |         |                 |                               |                        |
| Pharmacokinetic Sampling   |                       | X       | X |   | X  |         |   |         |         |                 |                               |                        |
| Biomarker Sampling   |                       | X       |   |   | X  |         |   | X       |         |                 |                               |                        |
| Pregnancy Test (Serum)   | X                     |         |   |   |    |         |   |         |         |                 |                               |                        |
| ECOG Performance Status  | X                     | X       |   |   |    | X       |   | X       | X       | X               |                               |                        |
| CT Chest/Abdomen/Pelvis    | X                     |         |   |   |    |         |   |         | X       | X   |                               |                        |
| Study Drug Reconciliation   |                       |         |   |   |    | X       |   | X       | X       | X               | X                             |                        |
| Concomitant Medications  | X        | X       |   | X | X  | X       | X | X       | X       | X               | X                             |                        |
| Survival Assessment  |                       |         |   |   |    |         |   |         |         |                 |                               | X                      |
| Adverse Events   |                       | X       |   | X | X  | X       | X | X       | X       | X               | X                             |                        |

1 Performed within 2 weeks prior to first dose of study drug.

2 Follow-up safety evaluations will occur 30 days ( $\pm$  7 days) after last dose of study drug. In the case of persistent drug-related toxicity, patients will be followed every 28 days until resolution or satisfactory stabilization is achieved. Telephone contact is acceptable.

| Evaluation | Baseline  | Cycle 1 |   |   |    | Cycle 2 |   | Cycle 3 | Cycle 4 | Further Cycles | End of Treatment  | Follow-Up  |
|------------|-----------------------|---------|---|---|----|---------|---|---------|---------|----------------|-------------------------------|------------------------|
|            |                       | 1       | 2 | 8 | 15 | 1       | 8 | 1       | 1       |                |                               |                        |
| Day        |                       | 1       | 2 | 8 | 15 | 1       | 8 | 1       | 1       | 1              |                               |                        |

- 3 Medical record review every 6 months to assess overall survival.
- 4 Height collected at baseline only.
- 5 Hematology ( complete blood count (CBC) with automated differentials)
- 6 Chemistry (complete metabolic panel (CMP): chloride, CO2, potassium, sodium, BUN, glucose, calcium, creatinine, total protein, albumin, total bilirubin, alkaline phosphatase, AST, ALT, A/G ratio, BUN/creatinine ratio, osmol (Calc), anion gap).
- 7 Pharmacokinetic samples and biomarker samples will be collected according to **Section 8.10** and **Section 8.11**, respectively.
- 8 For women of child-bearing potential only.
- 9 Baseline imaging within 4 weeks prior to treatment start. Additional scans will be taken every 9 weeks after cycle 1 –day 1 (± 7days). CT chest + MRI abdomen/pelvis is acceptable for disease assessment, if patients are unable to undergo a contrast enhanced CT.
- 10 Medications ongoing, or stopped, within 1 week prior to first dose of study drug.
- 11 CEA is to be performed every 3 cycles from cycle 4 onward (i.e. cycle 4, 7, 10...)
- 12 Study drug reconciliation from previous cycle, prior to starting new cycle.

**Table 12 Phase II: Schedule of Procedures and Observations**

| Evaluation   | Baseline  | Cycle 1 |   |    | Cycle 2 | Cycle 3 | Cycle 4 | Further Cycles  | End of Treatment  | Follow-Up  |
|--|-----------------------|---------|---|----|---------|---------|---------|-----------------|-------------------------------|------------------------|
|  |                       | 1       | 2 | 15 | 1       | 1       | 1       | 1               |                               |                        |
| Medical History  | X                     |         |   |    |         |         |         |                 |                               |                        |
| Pre-Existing Conditions  | X                     |         |   |    |         |         |         |                 |                               |                        |
| Physical Examination , including vital signs (i.e., temperature, heart rate, respiratory rate, blood pressure, body weight, and height)  | X                     | X       |   |    | X       | X       | X       | X               | X                             |                        |
| Hematology   | X                     | X       |   |    | X       | X       | X       | X               | X                             |                        |
| Chemistry    | X                     | X       |   |    | X       | X       | X       | X               | X                             |                        |
| INR/PT, PTT  | X                     |         |   |    |         |         |         |                 |                               |                        |
| CEA  |                       | X       |   |    |         |         | X       | X  |                               |                        |
| Urine Sample for Urine Protein Creatinine Ratio (UPCR)   | X                     |         |   |    |         |         |         |                 |                               |                        |
| Pharmacokinetic Sampling   |                       | X       | X | X  |         |         |         |                 |                               |                        |
| Biomarker Sampling   |                       | X       |   | X  |         | X       |         |                 |                               |                        |
| Pregnancy Test (Serum)   | X                     |         |   |    |         |         |         |                 |                               |                        |
| ECOG Performance Status  | X                     | X       |   |    | X       | X       | X       | X               |                               |                        |
| CT chest/abdomen/pelvis    | X                     |         |   |    |         |         | X       | X   |                               |                        |
| Study Drug Reconciliation   |                       |         |   |    | X       | X       | X       | X               | X                             |                        |
| Concomitant Medications  | X        | X       |   | X  | X       | X       | X       | X               | X                             |                        |
| Survival Assessment  |                       |         |   |    |         |         |         |                 |                               | X                      |
| Adverse Events   |                       | X       |   | X  | X       | X       | X       | X               | X                             |                        |

| Evaluation | Baseline  | Cycle 1 |   |    | Cycle 2 | Cycle 3 | Cycle 4 | Further Cycles | End of Treatment  | Follow-Up  |
|------------|-----------------------|---------|---|----|---------|---------|---------|----------------|-------------------------------|------------------------|
|            |                       | 1       | 2 | 15 | 1       | 1       | 1       | 1              |                               |                        |
| Day        |                       | 1       | 2 | 15 | 1       | 1       | 1       | 1              |                               |                        |

- 1 Performed within 2 weeks prior to treatment start.
- 2 Follow-up safety evaluations will occur 30 days ( $\pm$  7 days) after last dose of study drug. In the case of persistent drug-related toxicity, patients will be followed every 28 days until resolution or satisfactory stabilization is achieved. Telephone contact is acceptable.
- 3 Medical record review every 6 months to assess overall survival.
- 4 Height collected at baseline only.
- 5 Hematology ( complete blood count (CBC) with automated differentials)
- 6 Chemistry (complete metabolic panel (CMP): chloride, CO2, potassium, sodium, BUN, glucose, calcium, creatinine, total protein, albumin, total bilirubin, alkaline phosphatase, AST, ALT, A/G ratio, BUN/creatinine ratio, osmol (Calc), anion gap).
- 7 Pharmacokinetic samples and biomarker samples will be collected according to **Section 8.10** and **Section 8.11**, respectively.
- 8 For women of child-bearing potential only.
- 9 Baseline imaging within 4 weeks prior to treatment start. Additional scans will be taken every 9 weeks after cycle 1 –day 1 ( $\pm$  7days). CT chest + MRI abdomen/pelvis is acceptable for disease assessment, if patients are unable to undergo a contrast enhanced CT.
- 10 Medications ongoing, or stopped, within 1 week prior to first dose of study drug.
- 11 CEA is to be performed every 3 cycles from cycle 4 onward (i.e. cycle 4, 7, 10...)
- 12 Study drug reconciliation from previous cycle, prior to starting new cycle.

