### **6.8 Treatment Discontinuation**

Upon treatment discontinuation all end of treatment evaluations and tests will be conducted. All participants who discontinue due to an AE must be followed until the event resolves or stabilizes. Appropriate medical care should be provided until signs and symptoms have abated, stabilized, or until abnormal laboratory findings have returned to acceptable or pre-study limits. The final status of the AE will be reported in the participant's medical records and the appropriate eCRF.

Reasons for treatment discontinuation should be classified as follows:

- Death
- Progressive disease
- Toxicity; related or unrelated toxicity
- Investigator judgment
  - The Investigator may discontinue a participant if, in his/her judgment, it is in the best interest of the participant to do so.
- Noncompliance
- Participant voluntary withdrawal
  - A participant may withdraw from the study at any time, for any reason. If a participant discontinues treatment, an attempt should be made to obtain information regarding the reason for withdrawal.
- Boehringer Ingelheim decision
- NCCN decision

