**Table 16 Guidelines for Routine Adverse Event Reporting Phase 2 Studies (Regardless of Expectedness)**

| Attribution | Grade 1 | Grade 2 | Grade 3 | Grade 4 |
|-------------|---------|---------|---------|---------|
| Unrelated   |         |         | X       | X       |
| Unlikely    |         |         | X       | X       |
| Possible    | X       | X       | X       | X       |
| Probable    | X       | X       | X       | X       |
| Definite    | X       | X       | X       | X       |

Routine AEs occurring from the date the participant signs the study consent until 30 days after the last intervention or until the event has resolved, the study participant is lost to follow-up, the start of a new treatment, or until the study investigator assesses the event(s) as stable or irreversible, will be reported. New information will be reported after it is received.

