#### 10.3.2 Reporting Serious Adverse Events

All new SAEs occurring from the date the participant signs the study consent until 30 days after the last intervention or a new treatment is started, whichever comes first, will be reported. The RPCI SAE Source Form is to be completed with all available information, including a brief narrative describing the SAE and any other relevant information.

SAEs occurring after the 30 day follow-up period that the investigator determines to be possibly, probably or definitely related to the study intervention should be reported.

SAEs identified as an Unanticipated Problem by the Investigator must be reported. Please refer to Section 10.6 for details on reporting Unanticipated Problems.

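### The end-of-treatment safety visit may fall up to 7 days before adverse event reporting closes, and no contact on or after day 30 is scheduled for every patient

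*Combined protocol and SAP*

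**What the plan says.** **Visit timing.** The title of Section 8.7 reads "Evaluations Performed at End of Treatment (30 +/- 7 days post last dose of study drug", and footnote 2 of Table 11 (Phase I) and Table 12 (Phase II) gives the same window: "Follow-up safety evaluations will occur 30 days" after the last dose, with 7 days either way. Section 6.8 gives no day: "Upon treatment discontinuation all end of treatment evaluations and tests will be conducted".

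**Reporting period.** Section 10.3.2 has new SAEs reported from consent "until 30 days after the last intervention or a new treatment is started, whichever comes first". In Section 10.2.2, the sentence under Table 16 has routine AEs reported "until 30 days after the last intervention or until the event has resolved" and goes on to list further end points, one of which is the start of a new treatment.

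**Other follow-up.** Two groups have more. Footnote 2 continues: "In the case of persistent drug-related toxicity, patients will be followed every 28 days until resolution or satisfactory stabilization is achieved", and telephone is accepted for this. Section 6.8 adds: "All participants who discontinue due to an AE must be followed until the event resolves or stabilizes". For everyone else, the Follow-Up column of both tables marks only the survival assessment, which Section 8.8 defines as a medical record review every 6 months.

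**General statements.** Section 12.5 describes continuous safety monitoring that takes in a 30-day follow-up, but attaches no visit or call to the end of it. Section 10.3.2 keeps SAEs reportable after day 30 if the investigator judges them related.

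**The concern.** The visit window is centred on the day on which the reporting period ends, so its early half closes scheduled ascertainment before reporting closes. A patient who stops for progression, is seen on day 23 and has no ongoing drug-related toxicity meets every scheduled requirement. Nobody is then required to ask about days 24 to 30. The reporting clocks do not make up for this. Those in Section 10.4 run from receipt of the report, and the one-business-day notice in Appendix A runs from the site's awareness, so neither starts for an event that has not come to light.

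Toxicity of the regimen is a secondary objective of Phase II, and the Rationale calls the combination novel. At stake is how completely late AEs and SAEs are ascertained, and how promptly SAEs reach the sponsor.

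**Working it through.** **Inputs**

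- Visit day V after the last dose: 30 − 7 = 23 to 30 + 7 = 37 (Section 8.7; footnote 2 of Tables 11 and 12).
- End of reporting: day 30 (Sections 10.2.2 and 10.3.2), or the day S on which new treatment starts, if earlier (explicit for SAEs in 10.3.2).
- Scheduled AE contact for all patients after V: none (Section 8.8; Follow-Up column).

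The plan states no figure for a gap, so there is none to reproduce.

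**Formula.** Days of the reporting period after the last scheduled contact = max(0, min(30, S) − V). With no new treatment this is max(0, 30 − V).

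| Visit day V | New treatment S | Days without scheduled contact |
|---|---|---|
| 23 | none by day 30 | 30 − 23 = 7 |
| 30 | none by day 30 | 0 |
| 37 | none by day 30 | 0 (asked in retrospect) |
| 23 | day 26 | 26 − 23 = 3 |
| 23 | day 20 | 0 (period already closed) |

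**Worst case.** 7 of 30 days = 23% of the post-treatment reporting period.

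**Share of the window.** Days 23 to 37 are 15 permitted days. Days 23 to 29 are 7 of them, so 7/15 = 47% precede day 30.

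**Average under an even spread (assumption).** (7 + 6 + 5 + 4 + 3 + 2 + 1)/15 = 28/15 = 1.9 days, or 1.9/30 = 6% of the period. The documents give no distribution of visit days. The average can lie anywhere from 0 (all visits on or after day 30) to 7 days (all on day 23).

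**The other tolerance.** The note in Section 8.9 gives a general ±3 days for procedures after cycle 1 day 2. If that applied instead of ±7, the earliest visit would be day 27 and the largest gap 30 − 27 = 3 days. The specific ±7 is used above.

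**Patients with persistent drug-related toxicity.** After a day-23 visit the next 28-day contact is due about day 23 + 28 = 51, which covers days 24 to 30 in retrospect.

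**Scale of one missed patient.** In the Phase II set, 1/36 = 2.8 percentage points on a toxicity rate. Section 12.3 expects 90% interval widths of about 17 to 26 points.

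**The case against.** The strongest reply is that a visit window is not the reporting period. Sections 10.2.2 and 10.3.2 require reporting to day 30 wherever the visit falls, Section 12.5 promises continuous monitoring, and Appendix A schedules weekly or bi-weekly teleconferences on participants' adverse events. This stands in part: an event that reaches the site by day 30 must be reported. But the teleconferences are between staff, and none of these provisions requires anyone to contact the patient. What is missing is the prompt, not the duty.

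It is also true that the gap does not apply to every patient. Those with persistent drug-related toxicity have the 28-day contacts, and those who stopped for an AE are followed for that event.

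A reader might infer more than the documents support:

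- *All 30 days could be uncovered.* This reads Section 6.8 as placing the evaluations on the day of stopping. Section 6.8 names no day, while Section 8.7 and both tables time the same evaluations explicitly. The supported maximum is 7 days; 6.8 is loose wording to reconcile.
- *Visits after a switch of therapy contaminate the safety data.* Section 10.3.2 closes the new-SAE period when new treatment starts, and Section 10.2.2 lists that start as an end point. Onset dates are recorded (Section 10.4), and events can be attributed to other treatment (Section 10.2.1).
- *A 30-day toxicity rate or early-death count is truncated.* Section 12 contains no early-death count and gives the Wilson intervals no post-treatment window. Deaths are sought through the record review, so one may be learned of late but is not left to chance.

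**Conclusion.** The mismatch is real but minor. For a patient seen before day 30 who has no persistent drug-related toxicity, did not discontinue for an AE and has not started new treatment, up to 7 days of the reporting period have no scheduled contact. The 7-day maximum follows directly from the protocol; the 1.9-day mean rests on the assumed even spread of visits. The result takes day 30 as the close of routine AE reporting, although that sentence lists alternative end points. The number of events missed cannot be estimated, because the documents give no post-treatment AE rate.

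The consequence is possible slight under-ascertainment or late reporting of AEs and SAEs in a descriptive analysis. The 18-week PFS endpoint, the 36 patients, alpha and power do not depend on this visit.

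**What to change.** In Section 8.7 and footnote 2 of Tables 11 and 12, require AE and SAE collection to close at a contact on days 30 to 37 after the last dose, or just before new anticancer treatment if that comes first. Accept a telephone call, as the footnote already does for persistent toxicity. A site that prefers to keep the ±7-day visit could add a call only for patients seen before day 30. In Section 6.8, replace the undated instruction with a reference to the 8.7 timing, and state that the general ±3 days in Section 8.9 does not apply to this visit.

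No patient would then have an unscheduled remainder of the reporting period. The cost is protocol wording, plus a visit moved by up to a week or one phone call for some patients. Patients who switch therapy early would have the contact brought forward.
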